2. General study from EOT visit to last follow-up visit: To assess the change in corneal findings after discontinuation of study treatment, among eyes and subjects (worse eye) with exam finding at EOT visit worse than baseline, the following analyses will be performed.
- a. Summary of change (worsening, no change, improvement) from EOT to last follow-up visit based on categories defined below by eye (R/L) and subject (worse eye)
 - b. Summary of number (%) of eyes and subjects (worse eye) that resolve (improve to baseline level or better based on categories defined below), and descriptive summary of time from EOT visit to resolution among eyes and subjects (worse eye) that resolved

The parameters included in above analyses are:

1. BCVA change from baseline in log MAR scale (< 0.12 , ≥ 0.12 to < 0.3 , ≥ 0.3)
 2. IOP (≥ 22 mm Hg/ <22 mm Hg)
 3. Corneal epithelium (Normal/Abnormal), Punctate Keratopathy (None/Mild /Moderate/Severe), Corneal ulcer (No/Yes), Microcystic edema (No/Yes), Microcystic without edema (No/Yes), Subepithelial haze (No to Yes), Corneal neovascularization (No to Yes), Stroma (Normal/Abnormal); Active opacity (No/Yes); Active edema (No/Yes)
 4. Corneal endothelium (Normal/Abnormal), Descemet's folds (No/Yes; Peripheral/Central), Endothelial lesion (Peripheral/Central)
 5. Pachymetry (increase from baseline $< 5\%$, and $\geq 5\%$), Tear break up time (≤ 5 mm, > 5 and ≤ 10 mm, and > 10 mm), Schirmer's test (≤ 5 sec, > 5 and ≤ 10 sec, and > 10 sec)
3. Ocular sub-study (Cycle 1-4): To evaluate the effect of topical corticosteroids on corneal findings, pending on the availability of data, the following analyses will be performed in up to 30 participants who will receive monocular topical corticosteroids for the first 4 cycles:
- a. Summary of worst grade during Cycle 1-4 of corneal events (GSK scale) in eyes randomized to topical corticosteroids treatment and eyes not.
 - b. BCVA at baseline, at worst during Cycle 1-4, and worst and most frequent category (definite worsen, possible worsen, and no change/improved) of change from baseline during Cycle 1-4 will be summarized in eyes randomized to topical corticosteroids treatment and eyes not. Eyes with a decline in BCVA to 'light perception' (LP) or 'no light perception' (NLP) due to corneal finding anytime post-baseline will also be summarized.

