15.7.2. Handling of Missing Data

Element	Reporting Detail
General	
 • Missing data occurs when any requested data is not provided, leading to blank fields on the collection instrument: 
 ○ These data will be indicated by the use of a "blank" in subject listing displays. Unless all data for a specific visit are missing in which case the data is excluded from the table. ○ Answers such as "Not applicable" and "Not evaluable" are not considered to be missing data and should be displayed as such.
Outliers	
 • Any participants excluded from the summaries and/or statistical analyses will be documented along with the reason for exclusion in the clinical study report.
Responder Analysis	
 • For endpoints which determine the percentage of responders, subjects with unknown/not evaluable or missing best overall response will be assumed to be non-responders and will be included in the denominator when calculating the percentages.
Time to Event	
 • Because study treatment is dependent on the study endpoints (e.g., progression, i.e. not a fixed treatment duration), the length of treatment for each subject will depend on the efficacy and toxicity of the treatment, so the duration of treatment will vary across subjects. Similarly, the duration of follow up will also vary. All available time-to-event data will be analysed using suitable statistical methods; subjects with shorter treatment and follow-up due to the natural history of their disease or medical necessities of the treatment of their disease will not be considered to have missing time-to-event data.

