Table X
 Summary of Resolution Time from EOT in Best Corrected Visual Acuity (BCVA)

Parameter = Best Corrected Visual Acuity (BCVA)

	Treatment	Treatment
Right eye: n [1]	100	100
Number (%) of eyes that resolved [2]	50 (50%)	40 (40%)
Time from EOT Visit to resolution, days		
Mean	20.5	15.1
SD	1.44	1.24
Median	18	14
Min.	3	1
Max.	40	30
Left eye: n [1]	100	100
Number (%) of eyes that resolved [2]	50 (50%)	40 (40%)
Time from EOT Visit to resolution, days		
Mean	20.5	15.1
SD	1.44	1.24
Median	18	14
Min.	3	1
Max.	40	30
Subject (worse eye): n [1]	100	100
Number (%) of subjects that resolved [2]	50 (50%)	40 (40%)
Time from EOT Visit to resolution, days		
Mean	20.5	15.1
SD	1.44	1.24
Median	18	14
Min.	3	1
Max.	40	30

Note:

1: n is the number of eyes or subjects (worse eye) with exam result worse than baseline at EOT, which will be used as denominator to calculate the percentage.

2: Resolution is defined as improvement to baseline level or better.

Example SAFE_T4a

Protocol: 205678
 Population: Safety

Page 1 of 1
 (Data as of: 24APR2018)

Table X
 Summary of Resolution in Corneal Events (GSK Scale) during Follow-up Period

	Treatment Group A (N=100)	Treatment Group B (N=100)
n [1]	100	100
Number (%) of Participants that Resolve[2]	50 (50%)	40 (40%)
Time from EOT Visit to resolution[3], days		
Mean	20.5	15.1
SD	1.44	1.24
Median	18	14
Min.	3	1
Max.	40	30

Note:

- 1: n reflects the number of participants who had corneal event (GSK Scale) with grade worse than baseline at EOT
- 2: Resolution is defined as improvement to grade 1 or better
- 3: Calculated as the date of resolution minus the (last dose date +20 days).

Example SAFE_T4b
 Protocol: 205678
 Population: Safety

Page 1 of 1
 (Data as of: 24APR2018)

Table X

Summary of Time to Re-initiation of Study Treatment Post First Treatment Delay due to Corneal Events (GSK scale)

	Treatment Group A (N=100)	Treatment Group B (N=100)
Number (%) of subjects with treatment delay due to corneal event (GSK scale)	43	33
Re-initiation of study treatment	22 (51%)	19 (58%)
Time to re-initiation [1], days		
Mean	20.5	15.1
SD	1.44	1.24
Median	18	14
Min.	3	1
Max.	40	30

Note:

1: Time to re-initiation of study treatment is calculated as the date of first dose post treatment delay minus (the date of last dose prior to treatment delay +21).

Example SAFE_T5

Protocol: 205678
 Population: Safety

Page 1 of 1
 (Data as of: 24APR2018)

Table x.xxxx

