Outcome of first occurrence [1] (n=xx)			
Resolved	XX (XX.X%)	XX (XX.X%)	XX (XX.X%)
re-started with dose delay and reduction	XX (XX.X%)	XX (XX.X%)	XX (XX.X%)
re-started with dose delay but no reduction	XX (XX.X%)	XX (XX.X%)	XX (XX.X%)
re-started with dose reduction but no delay	XX (XX.X%)	XX (XX.X%)	XX (XX.X%)
re-started without dose delay or reduction	XX (XX.X%)	XX (XX.X%)	XX (XX.X%)
not re-started	XX (XX.X%)	XX (XX.X%)	XX (XX.X%)
Not resolved, re-started	XX (XX.X%)	XX (XX.X%)	XX (XX.X%)

CONFIDENTIAL

205678

with dose delay and reduction	XX (XX.X%)	XX (XX.X%)	XX (XX.X%)
with dose delay but no reduction	XX (XX.X%)	XX (XX.X%)	XX (XX.X%)
with dose reduction but no delay	XX (XX.X%)	XX (XX.X%)	XX (XX.X%)
without dose delay or reduction	XX (XX.X%)	XX (XX.X%)	XX (XX.X%)
Not resolved, not re-started	XX (XX.X%)	XX (XX.X%)	XX (XX.X%)
not discontinued	XX (XX.X%)	XX (XX.X%)	XX (XX.X%)
discontinued, follow up ongoing	XX (XX.X%)	XX (XX.X%)	XX (XX.X%)
discontinued, follow up ended	XX (XX.X%)	XX (XX.X%)	XX (XX.X%)
Duration of first occurrence [1] [2]			
n	XX	XX	XX
Mean	XX.X	XX.X	XX.X
SD	XX.XX	XX.XX	XX.XX
Median	XX.X	XX.X	XX.X
Min.	XX	XX	XX
Max.	XX	XX	XX
Number of occurrences (based on subjects with the event)			
One	XX (XX.X%)	XX (XX.X%)	XX (XX.X%)
Two	XX (XX.X%)	XX (XX.X%)	XX (XX.X%)
Three or more	XX (XX.X%)	XX (XX.X%)	XX (XX.X%)
Outcome post treatment exposure			
Number of of subjects with unresolved Event at the end of treatment exposure, or with event onset post treatment exposure.	xx	xx	xx
Resolved	XX (XX.X%)	XX (XX.X%)	XX (XX.X%)
Not resolved, follow up ongoing	XX (XX.X%)	XX (XX.X%)	XX (XX.X%)

Not resolved, follow up ended	XX (XX.X%)	XX (XX.X%)	XX (XX.X%)
Time to resolution post treatment exposure, days			
n	XX	XX	XX
Mean	XX.X	XX.X	XX.X
SD	XX.XX	XX.XX	XX.XX
Median	XX.X	XX.X	XX.X
Min.	XX	XX	XX
Max.	XX	XX	XX

[1] The duration is defined as time from onset of any **blurred vision** event to the first time the subject is free of any such event. It requires at least one day gap between the resolution of all events from first occurrence to the onset of second occurrence.

[2] Imputed AE stop date was used in the calculation of duration if the outcome of the event was resolved/resolved with sequelae and AE stop date was partial with day missing. Imputed AE start date was used in the calculation if the start date was partial with day missing.

[3] The end of treatment exposure is defined as last infusion date +20 days.

Programming note:

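### Time to resolution of ocular findings is described only among those that resolved, so the reported median is biased towards faster recovery and depends on length of follow-up

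*SAP*

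**What the plan says.** SAP Section 8.5 item 2 covers the period "General study from EOT visit to last follow-up visit" and is restricted to eyes and subjects (worse eye) whose finding at EOT is worse than at baseline. Item 2b has two parts. The first is a "Summary of number (%) of eyes and subjects (worse eye) that resolve". The second is a "descriptive summary of time from EOT visit to resolution among eyes and subjects (worse eye) that resolved".

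The shells in Appendix 14 follow this:

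- **SAFE_T4** (Tables 3.1110 to 3.1150) gives the number (%) resolved, then "Time from EOT Visit to resolution, days" as mean, SD, median, minimum and maximum. The denominator of the percentage is defined in a footnote: "n is the number of eyes or subjects (worse eye) with exam result worse than baseline at EOT". There is no count of censored eyes and no Kaplan-Meier estimate.
- **SAFE_T4a** has the same layout for corneal events on the GSK scale.
- **SAFE_T21** has a block headed "Time to resolution post treatment exposure, days". Its programming note computes the time from an AE end date or a first event-free date, so only resolved events can contribute. Rows just above it count events not resolved with follow-up ongoing or ended.
- **SAFE_T4b** does the analogous thing for restarting treatment after a corneal delay: "Time to re-initiation of study treatment is calculated as the date of first dose post treatment delay minus" the date on which the next dose would have been due. Only those who restart have a value.

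On follow-up, Section 15.7.2 says: "Similarly, the duration of follow up will also vary".

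**The concern.** A resolution time is seen only if it falls before that participant's last exam. Averaging the times that were seen cuts off the long ones, so the mean and median are too short whenever some findings remain unresolved. How much too short depends on how long people were followed, not only on how fast eyes recover.

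Section 8.5 item 2 exists to describe what happens to corneal findings once treatment stops, and ocular findings on exam are a listed endpoint under the secondary safety objective (Section 2.2). A reader of these tables is likely to take the median as the expected recovery time. Two groups with the same recovery but different follow-up would show different medians.

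**Working it through.** **The plan's own figure.** The SAP states no time to resolution (the shell numbers are placeholders), so there is nothing to reproduce. It also gives no length of ocular follow-up. What follows is illustrative, with assumptions shown as ranges.

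**Inputs from the SAP.** The time is summarised among the resolved only (8.5 item 2b). The denominator n is all those worse than baseline at EOT (SAFE_T4). Follow-up varies (15.7.2). Findings unresolved when follow-up ends are expected (8.2.3 item 59; SAFE_T21).

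**Assumptions.** Time to resolution is exponential with true median m. Follow-up after EOT is either a common length F or uniform between two limits, independent of resolution.

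**Common follow-up F.** The share resolved is p = 1 − 2^(−F/m). The median among the resolved is −ln(1 − p/2) × m / ln 2.

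For m = 90 and F = 90: p = 1 − 2^(−1) = 0.50, and the median is −ln(0.75) × 90/0.693 = 37.4 days.

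| F (days) | Resolved, m = 90 | Resolved-only median, m = 90 | Range for m = 60 to 150 |
|---|---|---|---|
| 42 | 28% | 19.3 | 18.5 to 20.0 |
| 90 | 50% | 37.4 | 33.8 to 40.4 |
| 180 | 75% | 61.0 | 49.8 to 71.8 |
| 365 | 94% | 82.4 | 58.7 to 113.2 |

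With 42 days of follow-up the statistic barely changes while the true median changes 2.5-fold (150/60). With 365 days it is close to the truth for m = 60 and m = 90, less so for m = 150.

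**Uniform follow-up between a and b.** The share resolved by time t is the integral from 0 to t of λe^(−λs) G(s) ds. Here λ = ln 2/m, and G(s) = 1 below a and (b − s)/(b − a) from a to b. The resolved-only median is the t at which this reaches half its final value.

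| Follow-up (days) | m = 90: resolved | m = 90: resolved-only median |
|---|---|---|
| 21-90 | 34% | 24 |
| 21-180 | 51% | 39 |
| 30-365 | 72% | 59 |

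With 21-90 days of follow-up, true medians of 60 and 180 days give 23 and 26 days.

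**After the fix.** A simulation of 200,000 draws used Kaplan-Meier with unresolved findings censored at end of follow-up:

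| Follow-up (days) | True median | Kaplan-Meier median | Resolved-only median |
|---|---|---|---|
| 21-365 | 60 | 59.9 | 45.5 |
| 21-365 | 90 | 89.8 | 58.2 |
| 21-365 | 150 | 149.8 | 73.5 |
| 21-120 | 60 | 59.6 | 27.0 |
| 21-120 | 90 | 90.0 | 29.7 |
| 21-120 | 150 | not reached | 32.3 |

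**Re-initiation (SAFE_T4b).** Permanent discontinuation and death prevent a restart, so they are competing events. Suppose restart and discontinuation have equal constant hazards h. The share who ever restart is h/(h + h) = 50%. One minus Kaplan-Meier with discontinuation censored is 1 − e^(−ht), which tends to 100%. Censoring at discontinuation or death would therefore overstate restarting.

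**The case against.** The strongest reply is that the summary is openly conditional and never stands alone. Item 2b says it is among those that resolved, and the same shell first gives the percentage resolved on the full denominator. That stands: non-resolution is not hidden. It does not remove the bias in the time. The percentage also depends on follow-up, the two figures together do not yield a median recovery time, and the row label in SAFE_T4 omits the condition.

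A second reply is that other displays deal with non-recovery:

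- change from EOT to last follow-up, including worsening (item 2a, Tables 3.1060 to 3.1100);
- the grade shift in Table 3.0410;
- updates on unresolved findings (8.2.3 items 38 to 42 and 45);
- time to last exam in the unrecovered (item 59);
- time-to-recovery plots (items 69 and 70).

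This is fair, and these displays reduce the harm. However, the plots state no method or censoring rule. They cover only corneal exam findings and keratopathy, not BCVA, intraocular pressure, endothelium, pachymetry or tear tests.

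Third, the follow-up sentence in Section 15.7.2 is general and is not about ophthalmic visits, whose schedule sits in the protocol. This stands as a limit on the size of the bias, not on its direction.

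A reader might infer two stronger points:

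- **That the group with shorter follow-up simply looks better.** The SAP does not support this. With a true median of 90 days, uniform follow-up of 21-90 rather than 30-365 days shortens the reported time (24 against 59 days) but also lowers the share resolved (34% against 72%), so that group looks worse on the line above.
- **That the median mostly measures follow-up.** This holds only in the short-follow-up scenarios. With a common 365 days it is 82 against a true 90.

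**Conclusion.** The point holds for Section 8.5 item 2b and for shells SAFE_T4, SAFE_T4a and the post-treatment block of SAFE_T21. The time to resolution they report is biased towards faster recovery whenever findings remain unresolved at the last exam, and it depends on follow-up length. The bias is negligible only if nearly all findings resolve within follow-up.

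The size is not determined by the SAP. For a true median of 90 days it runs from large (about 24 days reported) to small (about 82 days), resting on assumed exponential recovery and assumed follow-up. These are descriptive safety tables; the primary response-rate analysis is untouched. It is a worthwhile, inexpensive improvement rather than a critical flaw.

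SAFE_T4b is defensible as a summary among those who restarted, provided it is labelled so.

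**What to change.** **Section 8.5 item 2b, SAFE_T4, SAFE_T4a and SAFE_T21 (post-treatment block).** For all eyes or subjects in the existing denominator n, estimate time to resolution in one of two ways:

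- Kaplan-Meier, censoring unresolved findings at the last ophthalmic exam (for the AE-based events in SAFE_T21, at last follow-up); or
- cumulative incidence with death as a competing event.

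Report the median with 95% CI (stated as not reached where that applies), the proportion resolved at fixed times, and the number censored. Keep the resolved-only mean and median, if wanted, with a row label saying they are conditional on resolution.

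**SAFE_T4b.** Do not censor at discontinuation or death. If time to re-initiation is to be estimated, use cumulative incidence with permanent discontinuation and death as competing events, and censor only at the data cut. Otherwise keep the present summary, labelled as among those who re-initiated.

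**Cost.** SAP wording, shell and programming changes only; no new data. Kaplan-Meier is already used for duration of response, PFS, TTP, OS and time to treatment discontinuation. Reported recovery times will become longer or not reached, and for rare findings the medians may add little.

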2.3. Study Design

Overview of Study Design and Key Features	
	
 • Independent GSK2857916 Lyophilized Configuration Cohort 
 ○ Population: Subjects with relapsed/refractory MM (at least 25 subjects) ○ Objective: To assess the safety, efficacy, immunogenicity, and PK of GSK2857916 in a lyophilized configuration. • Ocular Sub-Study 
 ○ Population: Subjects with relapsed/refractory MM (up to 30 subjects (15 subjects each dose)) ○ Objective: evaluate the effect of topical corticosteroids on corneal findings in subjects who will receive monocular topical corticosteroids for the first 4 cycles and sign an optional ICF.
Dosing	
 • GSK2857916 Frozen Configuration Cohorts 
 ○ GSK2857916 will be administered at a calculated dose of 2.5 mg/kg or 3.4 mg/kg as an IV infusion over at least 30 minutes at the study sites. ○ Independent GSK2857916 Lyophilized Configuration Cohort 
 ○ GSK2857916 will be administered at a calculated dose of 3.4 mg/kg as an IV infusion over at least 30 minutes at the selected study sites when the lyophilized configuration becomes available. ○ Lyophilized configuration cohort will be initiated at 2.5 mg/kg if the results of the IA indicate that 3.4 mg/kg should not be continued. .
Time & Events	
 • Refer to Appendix 2: Schedule of Activities
Treatment Assignment	
 • This is a two-arm, randomized, multi-center, open-label study for GSK2857916 frozen configuration cohort. • For independent lyophilized cohort, there is only one dose group
Interim Analysis	
GSK2857916 Frozen Configuration Cohorts
 
 • One interim analysis (IA) is planned for the primary endpoint ORR after approximately 25 participants per arm are evaluable for response. Further details can be referred to in Section 3 of RAP and Section 4.1 of the protocol (Version: GSK Document Number TMF-13990464).

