5. CONSIDERATIONS FOR DATA ANALYSES AND DATA HANDLING CONVENTIONS

5.1. Study Treatment & Sub-group Display Descriptors

Treatment Group Descriptions			
RandAll NG		Data Displays for Reporting	
Code	Description	Description	Order in TLF
B	2.5 mg/kg frozen liquid solution of GSK2857916	2.5 mg/kg	1
A	3.4 mg/kg frozen liquid solution of GSK2857916	3.4 mg/kg	2
C	lyophilized configuration of GSK2857916	3.4 mg/kg Lyo, actual dose level subject to IA result	3
L	receive topical corticosteroids in left eye only	"3.4 mg/kg treated eye" for the treated eyes of participants in 3.4 mg/kg group (frozen liquid);	4
		"3.4 mg/kg untreated eye" for the untreated eyes of participants in 3.4 mg/kg group (frozen liquid)	5
R	receive topical corticosteroids in right eye only	"2.5 mg/kg treated eye" for the treated eyes of participants in 2.5 mg/kg group (frozen liquid);	6
		"2.5 mg/kg untreated eye" for the untreated eyes of participants in 2.5 mg/kg group (frozen liquid).	7

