 - c. Summary of onset time to first study treatment (BCMA)-related corneal finding (GSK scale) in eyes randomized to topical corticosteroids treatment and eyes not.
 - d. Summary of onset time to initiation of topical corticosteroids treatment in eyes randomized to no such treatment.
 - e. Shift in corneal findings (per ocular exam) from baseline to worst during Cycle 1- 4 in eyes randomized to topical corticosteroids treatment and eye not. Corneal findings include Corneal epithelium (Normal to Abnormal), Punctate Keratopathy (None/Mild to Moderate/Severe), Corneal ulcer (No to Yes), Microcystic edema (No to Yes), Microcystic without edema (Yes to No), Subepithelial haze (No to Yes), Corneal neovascularization (No to Yes), Stroma (Normal to Abnormal), Active opacity (No to Yes), and Active edema (No to Yes).

The details of the planned displays are provided in [Appendix 13](#): List of Data Displays.

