3.1180	Ocular Sub-Study	Mock-up SAFE_T18	Summary of Onset Time to First Drug-Related Corneal Event (GSK Scale) by Randomized Topical Corticosteroids Treatment		SAC [1]

Safety: Tables					
No.	Population	IDSL / Example Shell	Title	Programming Notes	Deliverable [Priority]
3.1190	Ocular Sub-Study	Mock-up SAFE_T19	Summary of Onset Time to Initiation of Topical Corticosteroids Treatment in Eyes Not-Randomized to Topical Corticosteroids Treatment		Headline, SAC [1]
3.1200	Ocular Sub-Study	Mock-up SAFE_T20	Shift in Corneal findings (per Ocular Exam) from Baseline to Worst during Cycle 1-4 by Randomized Topical Corticosteroids Treatment		SAC [1]

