No.	Population	IDSL / Example Shell	Title	Programming Notes	Deliverable [Priority]
Anti-Drug Antibody					
30.0180	Full Safety	Programming note	Listing of Human Anti-GSK2857916 Antibody Results	See Listing 30.0620 from BMA117159 (primary_01) with following change: 1. Add a new column 'Neutralizing Antibody Assay' between TITER and ADC Concentration. The result will be either 'POSITIVE' or 'NEGATIVE'. 2. Add a note: Neutralizing Antibody Assay was only applied to confirmed ADA positive samples.	SAC [1], SAC [2]
Corneal Events (GSK Scale)					
30.0190	Full Safety	Mock up SAFE_L2	Listing of Corneal Events (GSK Scale)	List corneal findings by eye R/L and patient as well as action taken with study treatment.	SAC [1], SAC [2]
30.0191	Full Safety	Programming note	Listing of Resolution in Grade of Corneal Events (GSK Scale) for each Corneal Event in patients experiencing >1 event	See 30.0192 in present_2020_04	SAC [2]
30.0200	Ocular Sub-Study	Mock up SAFE_L2	Listing of Corneal Events (GSK Scale) in Ocular Sub-Study Subjects	List corneal findings by eye R/L and patient as well as action taken with study treatment. When break down by treatment arm, also included the information on which eye is randomized to corticosteroids (e. g Eye randomized to topical corticosteroids treatment = L.)	SAC [1], SAC [2]
8.0102	Full Safety	Programming note	Listing of BCVA for patients who gave up driving due to eyesight	Refer present_2020_04	SAC [2]

CONFIDENTIAL

205678

Non-ICH: Listings					
No.	Population	IDSL / Example Shell	Title	Programming Notes	Deliverable [Priority]
8.0103	Full Safety	Programmin g note	Listing of BCVA for patients who experienced difficulty reading newspapers due to eyesight	Refer present_2020_04	SAC [2]
Ocular Exam					
30.0210	Full Safety	Programmin g note	Listing of Visual Acuity and Abnormal Corneal Exam Results	See Listing 30.0260 from BMA117159 (primary_01)	SAC [1]
30.0220	Full Safety	Programmin g note	Listing of Abnormal Conjunctival Exam Results	See Listing 30.0330 from BMA117159 (primary_01)	SAC [1]
30.0230	Full Safety	Programmin g note	Listing of Abnormal Slit Lamp Anterior Chamber, Slit Lamp Iris, and Slit Lamp Lens Exam Results	See Listing 30.0210 above	SAC [1]
30.0240	Full Safety	Programmin g note	Listing of Abnormal Dilated Fundoscopic Exam Results	See Listing 30.0210 above	SAC [1]
Health Outcome					
30.0250	Full Analysis	VS4	Listing of EORTC QLQ-C30 Scores	use collected visit dates. List overall summary score and 14 domain scores	SAC [1]

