Note: No change/improved vision is defined as a change from baseline <0.12; a possible worsened vision is defined as a change from baseline >=0.12 to <0.3; a definite worsened vision is defined as a change from baseline >=0.3 logMAR score.

Example SAFE_T18
 Protocol: 205678
 Population: Safety

Page 1 of 1
 (Data as of: 24APR2018)

Table x.xxxx

Summary of Onset Time to First Drug-Related Corneal Event (GSK Scale) by Randomized Topical Corticosteroids Treatment

	Treatment Group A (N=xx)		Treatment Group B (N=xx)	
	Eyes randomized to corticosteroids	Eyes randomized to no corticosteroids	Eyes randomized to corticosteroids	Eyes randomized to no corticosteroids
Number (%) of eyes experienced drug-related corneal event (GSK scale)	5 (50%)	4 (40%)	4 (40%)	5 (50%)
Time to initiation, days				
n	5	5	5	5
1-21	1 (20%)	1 (20%)	1 (20%)	1 (20%)
22-42	2 (40%)	2 (40%)	2 (40%)	2 (40%)
43-63	1 (20%)	1 (20%)	1 (20%)	1 (20%)
> 63	1 (20%)	1 (20%)	1 (20%)	1 (20%)
Mean	20.5	15.1	15.1	20.5
SD	1.44	1.24	1.24	1.44
Median	18	14	14	18
Min.	3	1	1	3
Max.	40	30	30	40

Example SAFE_T19
 Protocol: 205678
 Population: Ocular Sub-Study

Page 1 of 1
 (Data as of: 24APR2018)

Table x.xxxx

Summary of Onset Time to Initiation of Topical Corticosteroids Treatment in Eyes Not Randomized to Topical Corticosteroids Treatment

	Treatment Group A (N = xx)	Treatment Group B (N = xx)
Number (%) of eyes that initiated topical Corticosteroids Treatment	5 (50%)	4 (40%)
Time to initiation, days		
n	5	5
1-21	1 (20%)	1 (20%)
22-42	2 (40%)	2 (40%)
43-63	1 (20%)	1 (20%)
> 63	1 (20%)	1 (20%)
Mean	20.5	15.1
SD	1.44	1.24
Median	18	14
Min.	3	1
Max.	40	30

Note:

1: N reflects the number of eyes randomized to no topical corticosteroids treatment for ocular sub-study.

Example SAFE_T20
 Protocol: 205678
 Population: Safety

Page 1 of 1
 (Data as of: 24APR2018)

Table x.xxxx
 Shift in Corneal Events (per Ocular Exam) from Baseline to Worst During Cycle 1-4 by Randomized Topical
 Corticosteroids Treatment

Exam	Shift from Baseline to Worst (Cycle 1-4)	Treatment Group A (N = xx)		Treatment Group B (N= xx)	
		Eyes randomized to corticosteroids	Eyes not randomized to corticosteroids	Eyes randomized to Corticosteroids	Eyes not randomized to corticosteroids
Corneal Epithelium	n	100	100	100	100
	Normal to Normal	30 (30%)	30 (30%)	30 (30%)	30 (30%)
	Normal to Abnormal	50 (50%)	50 (50%)	50 (50%)	50 (50%)
	Abnormal to Normal	0	0	0	0
	Abnormal to Abnormal	20 (20%)	20 (20%)	20 (20%)	20 (20%)

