	Change from Baseline	n	xx	xx	xx
		Mean	x.x	x.x	x.x
		SD	x.xx	x.xx	x.xx
		Median	x.x	x.x	x.x
		Min	x.x	x.x	x.x
		Max	xx.x	xx.x	xx.x

[figure not shown]
Example: PRO_F1
Protocol: 205678
Population: Safety

Page 1 of 1
(Data as of: 30MAY2001)

Figure x.xxxx

Stacked Bar Chart of PRO-CTCAE Score by Attributes and Visit

Item X

Programming note: There is flexibility in choosing colour.

Example SAFE_L2
 Protocol: 205678
 Population: Safety

Page 1 of 1
 (Data as of: 24APR2018)

Listing X
 Listing of Corneal Findings (GSK Scale)

Treatment Group A

Centre Id/ Subj.	Age (y) / Sex/ Race	Eye	Grade/ Exam Finding(s)	Overall Grade of Corneal Examination Findings/Visual Acuity Grade/Overall Grade for GSK Scale for this eye	Date of Assessment /Visit	Time Since 1st Dose/ Last Dose	Action(s) Taken with study treatment/ Related
PPD [redacted]	PPD [redacted]	Left	Grade 2/ Moderate keratopathy, Grade 3/Diffuse Epithelial or stromal edema	Grade 3/ Not Applicable/ Grade 3	PPD [redacted] / Week 4	15 d/ 10 d	Dose reduced, Dose interrupted/delaye d/ No
		Right	Grade 3/ Diffuse microcysts	Grade 3/ Grade 1/ Grade 3	PPD [redacted] / Week 4	30 d/ 0 d	Dose interrupted/delaye d/ Yes
		Left	Grade 1/Mild superficial keratopathy	Grade 1/ Not Applicable/ Grade 1	PPD [redacted] / Week 7	32 d/ 0 d	Dose interrupted/delaye d / No
		Right	Grade 1/Mild superficial keratopathy	Grade 1/ Not Applicable/ Grade 1	PPD [redacted] / Week 7	32 d/ 0 d	Dose interrupted/delaye d /No

Treatment Group B

 Treatment Group C

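### The ocular sub-study's only onset analysis counts just the corneal findings judged related to GSK2857916, although its objective covers corneal findings whatever their cause

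*SAP*

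**What the plan says.** Section 2.2 gives the sub-study objective as evaluating how topical corticosteroids affect corneal findings. Its endpoint is a description of differences in corneal findings between the eyes, taken from ophthalmic examinations. Neither mentions attribution to GSK2857916.

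Section 8.5, item 3c, plans a "Summary of onset time to first study treatment (BCMA)-related corneal finding (GSK scale"), for eyes randomized to the steroid and for eyes not so randomized. The display list (Section 15.13.8) carries this forward as Table 3.1180, "Summary of Onset Time to First Drug-Related Corneal Event (GSK Scale) by Randomized Topical Corticosteroids Treatment". Shell SAFE_T18 in Appendix 14 applies the restriction to the count as well as to the timing; its first row is "Number (%) of eyes experienced drug-related corneal event (GSK scale").

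The contrast is within participant: Section 5.1 codes the allocation by eye, for example "receive topical corticosteroids in left eye only". Section 2.3 says of the dose comparison: "This is a two-arm, randomized, multi-center, open-label study for GSK2857916 frozen configuration cohort". It gives the sub-study size as up to 30 participants, 15 at each dose.

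**The concern.** The sub-study compares steroid with no steroid. GSK2857916 is given intravenously, so both eyes are exposed to it. Deciding whether a finding is due to GSK2857916 is a judgement made after randomization, and it could depend on the other exposure, the drops, which only one eye receives. If attribution differs between treated and untreated eyes, eyes with the same findings are counted differently. An eye whose earliest corneal change is called unrelated either drops out of the count or enters later, once a corneal change is called related.

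At stake is the only sub-study summary that says when corneal findings begin. Item 3d is also a time summary, but it times the start of steroid drops in eyes not randomized to them. Items 3a, 3b and 3e describe corneal and visual outcomes over Cycles 1 to 4 but carry no onset time.

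**Working it through.** **Objective against event definition.** The SAP states no sample size, power or expected rate for the sub-study, so there is no figure of its own to reproduce. The check starts with a comparison of the sub-study items:

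| Item | Display | Limited to drug-related findings? | Gives onset of a corneal finding? |
|---|---|---|---|
| Objective and endpoint, Section 2.2 | – | No | – |
| 3a worst GSK grade, Cycles 1–4 | Table 3.1160 | No | No |
| 3b visual acuity | Table 3.1170 | No | No |
| 3c onset | Table 3.1180, SAFE_T18 | **Yes** | **Yes** |
| 3d start of steroid drops in untreated eyes | Table 3.1190 | Not applicable | No |
| 3e shift in exam findings | Table 3.1200 | No | No |

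The one item that gives onset is the one filtered on relatedness.

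**At what level is relatedness recorded?** Listing 30.0190 and its sub-study counterpart 30.0200 are to "List corneal findings by eye R/L and patient as well as action taken with study treatment". The shell they share, SAFE_L2, has one row per eye, with a column "Action(s) Taken with study treatment/ Related". That layout suggests a per-eye entry, but no derivation rule confirms it. Per-eye attribution is therefore an assumption in what follows.

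**Sensitivity of one cell.** SAFE_T18 reports each dose separately, so each cell holds at most 15 eyes. One reclassified eye moves its percentage by 1/15 = 6.7 points. As an assumed example, let 9 of 15 eyes be affected in each group (60%). If three treated-eye findings are put down to another cause, the table shows 6/15 = 40% against 9/15 = 60%, with no true difference.

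**Illustration over a range, doses pooled.** Take 30 eyes per group and no true steroid effect. Let p be the share of eyes with any finding, and a the probability that an affected eye's finding is judged related. Then:

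- eyes counted = 30 × p × a
- spurious difference = p × (a untreated − a treated)

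For p = 60%, a = 80% in treated eyes and 95% in untreated eyes:

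- treated: 30 × 0.60 × 0.80 = 14.4 eyes
- untreated: 30 × 0.60 × 0.95 = 17.1 eyes
- difference: 0.60 × 0.15 = 9 points

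| a treated / a untreated | p = 40% | p = 60% | p = 80% |
|---|---|---|---|
| 100% / 100% | 0 | 0 | 0 |
| 90% / 100% | 4 | 6 | 8 |
| 80% / 95% | 6 | 9 | 12 |
| 70% / 95% | 10 | 15 | 20 |
| 95% / 80% | −6 | −9 | −12 |

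Entries are percentage points; positive means fewer treated eyes counted. All values of p and a are assumptions. The last row shows the sign reversing when attribution leans the other way. With an all-cause definition, attribution contributes 0 in every row.

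**The case against.** The text, display list and shell agree with each other, so the SAP does not contradict itself about what 3c will contain. Onset of drug-related findings is also a coherent question when the steroid is given alongside that drug. That stands as a reason to keep the drug-related count. It does not explain why the stated objective, corneal findings in each eye, has no onset summary of its own.

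Three stronger readings are tempting, and the document supports none of them.

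- **That relatedness is shown to differ between a participant's two eyes in an unmasked comparison.** SAFE_L2 does show No for the left eye and Yes for the right at Week 4. These are dummy entries: the two rows give 15 and 30 days since first dose, so they cannot depict one exam. The open-label statement describes the dose study. Masking of the eye assessor, and the attribution rule for GSK-scale findings, may be in the protocol, which is not shown; their absence here is not a defect.
- **That the bias favours the steroid.** Nothing in the SAP fixes the direction. Equal attribution gives no bias, and the opposite leaning reverses it.
- **That corneal harm from the steroid is hidden.** This table would leave out findings attributed to the drops, but 3a, 3b and 3e report outcomes by the same eye allocation with no filter on relatedness to study drug. Listing 30.0200 shows each eye's findings and which eye was randomized to steroid, and its shell includes time since first dose.

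The consequence is also modest: the sub-study is small and descriptive, with no hypothesis test or decision rule.

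**Conclusion.** The point holds for item 3c, Table 3.1180 and SAFE_T18 only. The sub-study's single analysis of time to a corneal finding selects events on a post-randomization attribution that its objective and endpoint do not call for. Any difference in attribution between eyes would carry straight into the comparison. The size is unknown: 0 if attribution is equal, and 4 to 20 points in either direction for gaps of 10 to 25 points with 40% to 80% of eyes affected. This rests on two assumptions that the SAP does not settle, namely that relatedness is assigned per eye and that whoever assigns it knows which eye receives the steroid. The other corneal summaries and every stated figure in the SAP are unaffected. It is a minor improvement to one descriptive table.

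**What to change.** Define the event in item 3c and Table 3.1180 as the first GSK-scale corneal finding worse than baseline, regardless of attribution, for both the number of eyes and the onset time. Keep the drug-related count as a supportive row in SAFE_T18. Table 3.1180 is tagged for the primary analysis only (SAC [1]), and Sections 9 and 12.2 already describe primary-analysis work in the past tense, so it may have been produced. If so, add the all-cause summary as a supplementary table, labelled as added later.

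The cost is a small amount of extra programming on one descriptive table. No new data are needed: findings by eye, time since first dose and the randomized eye are already planned for Listing 30.0200, which is due at both the primary and end-of-study deliveries.
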